### **B. Type of Data Evaluated**

Median daily pain score, and survey results.

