Following cesarean delivery, subjects will be re-approached in the Postpartum Unit at Robert Wood Johnson University Hospital by study staff. The TENS device will be again reviewed, and provided to the patient, with review of instructions for use. The patients in the intervention group will be educated on the proper way to utilize the TENS unit. They will apply the patches of the TENS unit above and below the C-section site. Specifically, the electrode patches will be placed above the abdominal bandages post-operatively and replaced above the abdominal bandages after the dressing change on post-operative day 1. Starting 8 hours after C-Section, the TENS unit will be turned on to a comfortable intensity as determined by the patient and will remain on until the patient is discharged, to be removed for toileting and showering and at the patient's discretion. Once the TENS unit is applied and turned on, the patient will not have to do anything else to maintain the therapy. Study staff will provide a record for documentation of time on/off for the unit. Additionally, a member of the study staff will check on the device daily to ensure proper maintenance. On the day of discharge, study staff will collect the device, and conduct a short survey about pain scores. They will then review pain scores, pain medication usage and other secondary outcomes in the patient's chart. Finally, pain will be reassessed at the subject's outpatient postpartum visits by study staff. The subjects will complete a measure of perceived physical disability at the outpatient postpartum visit.

**DATA COLLECTION.** Our research team members will collect the following data points from the patient's inpatient medical record: pain scale scores, medication requests/prescriptions (including name, type, and amount), time to first bowel movement, subjective incision site complaints, and time to OOB. Participants will complete a survey before discharge which will solicit additional information about the postpartum recovery experience with or without TENS therapy. (Survey is submitted with this protocol as Appendix A.) Participants will complete a survey at the 6-week postpartum visit on perceived difficulties because of health (The survey, WHODAS 2.0, is submitted with the protocol as Appendix B).

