#### **4.9 Risks to Subjects**

##### **A. Description of Subject Risk**

Research has shown that TENS therapy is a safe device when used appropriately after surgery. Minor tingling is normal during TENS therapy. However, some patients find the tingling sensation from the device to be uncomfortable when the intensity of the device is too high. If this occurs, the intensity may be turned down. In rare cases, patients have developed adverse skin irritation or rash at the sites where the electrodes are placed. There are no anticipated long-term complications to cesarean scar wound healing.

There is also the risk of loss of privacy. However, data will be associated with a subject study ID number, and protected health information will not be recorded.

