###### **▪ Risk Of Imposing An Intervention On Subject With Existing Condition**

Patients with known history of cardiac arrhythmia or pacemaker will be excluded. However, the subject will be instructed to stop use of the device and call the study staff if palpitations occur.

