### **4.11 Chart/Record Review Selection**

Data will be collected by [name]. It will be collected at the time of discharge survey conduct on the RWJUH postpartum floor. Items collected from the patient's flowsheets will include pain ratings and subjective incisional complaints, number and type of pain medications used, patient satisfaction with pain control, time to first bowel movement, level of sedation and time to OOB. This will be directly imputed into an Excel spreadsheet on the investigator's password protected laptop provided by the Rutgers IT department, without identifiers.

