## **6.3 Data and Safety Monitoring**

### **A. Periodic Data Evaluation**

Data will be evaluated after pairs of intervention and control subjects are enrolled to compare differences. If 3 consecutive sets of intervention/controls demonstrate worse outcomes for intervention subjects, the study will be suspended. Additionally, interim data analysis will be performed by the project statistician after enrollment of 50% of subjects to ensure that device usage does not cause increased pain.

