### **C. Collection of Safety Information**

Direct access into the EMR at discharge, conduct of survey with the patient.

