### **G. Tests for Safety Data**

Non-parametric analysis of median daily pain score.

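### Safety review is specified for pain scores and surveys only; no recording, count or review of electrode-site skin reaction, device discomfort or palpitations is specified in the available text

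*Protocol*

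**What the plan says.** Section 6.3.B of the protocol states what is evaluated in safety monitoring: "Median daily pain score, and survey results". The other review provisions follow the same line:

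- The test for safety data (6.3.G) is "Non-parametric analysis of median daily pain score".
- The interim analysis at 50% enrolment (6.3.A) is "to ensure that device usage does not cause increased pain".
- The safety review after the first 10 patients (1.3, endpoints paragraph) looks for scores that worsen relative to controls.
- The suspension rule (6.3.A, 6.3.H) depends on worse outcomes in three consecutive pairs, with no definition of outcome beyond the data types in 6.3.B.
- Section 6.3.C names the sources of safety information: "Direct access into the EMR at discharge, conduct of survey with the patient".

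The risk sections raise events of a different kind. Section 4.9.A says: "In rare cases, patients have developed adverse skin irritation or rash at the sites where the electrodes are placed". It also notes that tingling can be uncomfortable at too high an intensity, which may then be lowered. Section 4.9.D says that "the subject will be instructed to stop use of the device and call the study staff if palpitations occur", and 4.9.E adds an assessment for palpitations when the device is switched on.

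On data collection, section 4.11 says: "Items collected from the patient's flowsheets will include pain ratings and subjective incisional complaints". It goes on to medications, satisfaction, bowel movement, sedation and time out of bed. The list in 1.3 is similar. The SAP's outcomes are pain, medication, satisfaction, the 6-week surveys, bowel movement, sedation and time out of bed.

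**The concern.** The harms that the protocol itself raises and the data that it sends to safety review do not match. Someone who applies 6.3 as written is directed to pain scores and survey answers. A rash under an electrode, or palpitations that led a woman to switch the device off, need not change a daily median pain score, and nothing visible requires either to be written down as a study item.

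Two things are at stake. The reviewers named in 6.3.E may have no count of device events before them when they decide whether to continue. And a pilot that section 1.5 presents as the basis for larger trials might end without a device-event count to report. The withdrawal rule in 4.7.B adds to this: if consent is withdrawn during device use, no outcome data are collected and the device log is destroyed. A withdrawal prompted by such an event could therefore leave no study record.

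**Working it through.** **Step 1: trace each harm through the visible text.** There is no stated figure to reproduce, since section 6.1.B reports no power analysis and no event rates are given. The check is whether each harm has a management step, a recording item, a place in review and a place in the SAP.

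| Harm | Individual management | Recording item (1.3, 4.11) | Safety review (6.3.B, 6.3.G) | SAP |
|---|---|---|---|---|
| Skin irritation or rash (4.9.A) | none stated once it occurs | none | not listed | none |
| Uncomfortable tingling (4.9.A, 4.9.E) | teaching; lower intensity | none; the on/off record gives times, with no reason mentioned | not listed; acceptability questions (1.9.B) might touch on it | none |
| Palpitations (4.9.D, 4.9.E) | check at switch-on; stop and call | none | not listed | none |

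Section 6.3.C does not fill the empty cells. It names where information comes from, not which events are extracted, and the extraction lists in 1.3 and 4.11 contain none of the three. The nearest collected item is subjective incisional complaints, which is an outcome in 1.6.B but is absent from both 6.3.B and the SAP.

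**Step 2: what a count could show.** Section 1.5 gives 5 + 5 = 10 women on TENS. The true rates q are my assumptions; section 4.9.A calls skin reaction rare, so the lower rows suit it best. The chance of at least one event is 1 − (1 − q)^10.

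| Assumed q | Calculation | Chance of at least one event |
|---|---|---|
| 1% | 1 − 0.99^10 = 1 − 0.904 | 9.6% |
| 2% | 1 − 0.98^10 = 1 − 0.817 | 18.3% |
| 5% | 1 − 0.95^10 = 1 − 0.599 | 40.1% |
| 10% | 1 − 0.90^10 = 1 − 0.349 | 65.1% |

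If no event is seen, the one-sided 95% upper bound u solves (1 − u)^10 = 0.05, so u = 1 − 0.05^(1/10) = 1 − 0.741 = 25.9%.

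**Step 3: sensitivity to sample size.** Section 4.5.A gives 20 subjects and 4.5.C gives 40. If 40 meant 20 per arm, the chance of at least one event would be 18.2%, 33.2%, 64.2% and 87.8% at the same rates, and the upper bound for 0 of 20 would be 13.9%.

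**Step 4: can the arms be compared?** The daily contact in 1.3, where "a member of the study staff will check on the device daily to ensure proper maintenance", exists only for women with a device, and so does the switch-on check for palpitations. Anything sought at those contacts is looked for more often under TENS. Electrode-site reaction and stopping the device cannot occur in controls at all.

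**The case against.** The best reply is that the plan is wider than 6.3.B read alone. Survey results are among the reviewed data, and the survey asks about recovery and the acceptability of the device, so it may well include a question on skin or discomfort. Record access under 6.3.C is open-ended, and a charted rash or palpitation would be visible there. Women are checked at switch-on, told to stop and call, and may have the intensity lowered. The harms are described as rare or as precautions, and 10 treated women can support only description.

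Much of this stands. Appendix A and the schedule of events are not in the available text, so a relevant item in either cannot be ruled out. The individual safeguards are real. The small sample does limit any count to description.

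It does not close the gap. A source is not a data item, and looking after one patient does not give the reviewers a count. The survey components listed in 1.9.B are two pain questionnaires, acceptability questions and, at 6 weeks only, a disability scale; none is described as collecting adverse events. Whatever Appendix A contains, 4.11 and the SAP name no skin or palpitation item.

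**Conclusion.** The point holds as a gap in specification: the visible text calls for no recording, count or review of electrode-site skin reaction, device discomfort or palpitations, although the protocol raises all three. It should be corrected because it touches patient safety and is cheap to mend. It does not affect the pain comparison or the sample size.

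A reader might infer more than the documents support:

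- That these harms are never reviewed, or that monitoring cannot detect them. This is unproven, given the unseen survey and schedule, the record access and the bedside checks.
- That wound complications are a third named harm left unwatched. Section 4.9.A mentions scar healing only to say that no long-term complications are anticipated, and incisional complaints are collected.
- That the device is expected to cause these harms. Skin reaction is called rare, and palpitations appear as a precaution.

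The size of the gain is modest. With 10 TENS women, the chance that there is any event to record runs from about 10% to 65% over assumed rates of 1% to 10%, and a clean record would still be compatible with a rate of up to about 26%. These figures rest on the assumed rates, on 10 women with complete ascertainment, and on independence between women.

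**What to change.** - **Protocol 4.11 and 6.3.B:** add electrode-site skin reaction, palpitations, and device stopped for discomfort to the items collected and to the data reviewed. If Appendix A or the schedule already has such an item, cite it in both places.
- **TENS-arm counts:** record electrode-site reaction and device stopping at the existing daily device check and at discharge, and report them for the TENS arm only. Report palpitations found by the switch-on check in the same way.
- **Comparison by arm:** compare palpitations and the already collected incisional complaints only from sources applied identically to both arms, namely the discharge chart review and survey and the 6-week visit.
- **SAP:** add a descriptive safety listing with counts and denominators and no hypothesis test.
- **If enrolment is already complete:** search the records still held before the source data are destroyed under 6.1.E, and state in the report that these events were not collected systematically.

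Any threshold for clinical action is for the investigators to set. The cost is a few data fields at contacts that already take place. The limitation to accept is that the output will be descriptive only.

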### **C. Collection of Safety Information**

Direct access into the EMR at discharge, conduct of survey with the patient.

### **D. Frequency of Data Collection**

After each pair of intervention/control

### **E. Reviewer of Data**

[name], [name] and the statistician [name]

### **F. Schedule of Review of Cumulative Data**

Every 6 months

### **G. Tests for Safety Data**

Non-parametric analysis of median daily pain score.

### **H. Suspension of Research**

If 3 consecutive sets of intervention/controls demonstrate worse outcomes for intervention subjects, the study will be suspended.

## **6.4 Reporting Results**

### **A. Sharing of Results with Subjects**

Subjects will not be re-contacted to share results.

### **B. Individual Results**

None

### **C. Aggregate Results**

None

### **D. Professional Reporting**

Professional reporting will be at national conferences and journals in obstetrics and gynecology, as well as physical therapy.

### **E. ClinicalTrials.Gov Registration and Data Reporting**

This study will be reported to ClinicalTrials.gov

## **6.5 Data Sharing**

N/A

## **7.0 Data and/or Specimen Banking**

N/A

## **8.0 Other Approvals/Authorizations**

N/A

TENS and Opioid Use After Cesarean Delivery

NCT03843788

Document Type: Statistical Analysis Plan

Document Date: 7/11/2024

Statistical Analysis Plan

All outcomes will be presented using descriptive statistics; normally distributed data by the mean and standard deviation (SD) and skewed distributions by the median and interquartile range (IQR).

Primary Outcome

The primary analysis will compare intervention groups (TENS vs usual care) on mean change in pain score as measured by Visual Analog Scale (VAS) over the course of the inpatient hospital stay. Measured primary outcomes were pain ratings, number and type of pain medications used, and patient satisfaction with pain control. Fixed effects repeated measures analysis of variance was used to evaluate the differences in pain scores between groups and Mann-Whitney tests were used to examine differences in medication intake. Additionally, repeated measures correlation (RMCORR) between TENS and usual care arms with an exploratory analysis of pain behavior in individuals with SUD compared to no SUD will be performed.

Secondary outcomes

Secondary outcomes will include pain surveys at 6 weeks postoperatively, time to first bowel movement, level of sedation, and time to out-of-bed (OOB).

Missing data

Mixed-effects procedure was utilized to avoid loss of data from missing values at different time points.

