### **1.3 Research Design and Methods**

**OVERVIEW.** This study is a pilot randomized interventional trial. Two categories of participants will be randomly assigned to an invention or control group, using a random number generator: normal cesarean without associated comorbidity, or cesarean in women with a history of opioid addiction, as defined by use of opioid replacement medications of either methadone or Subutex during pregnancy. The control group will receive usual care which is

Version Number: 5

Protocol Number: Pro2018001008

PI Name: [name]

Protocol Title: TENS after Cesarean Delivery

4

RESERVED FOR IRB STAMP

DO NOT MODIFY THIS SPACE

IRB ID: Pro2018001008

[figure not shown]
IRB Form Version: 01/2018 Approval Date: 7/19/2022

Expiration Date: 7/18/2023

standard post-operative pain management with opioids and NSAIDS. The intervention group will receive usual care plus TENS therapy beginning 8 hours after C-section and continuing to discharge. Both groups will receive medications for pain as requested or ordered by the doctor.

**RESEARCH PROCEDURES.** Patients will be identified for participation in several locations. Prenatal patients at the Rutgers Medical Group Obstetrics and Gynecology or Maternal Fetal Medicine practices, or the High Risk Obstetric Perinatal Clinic will be approached for study inclusion. Physicians that have a direct treatment relationship with the patient will inform the patient about the study and invite them to enroll. Consent for participation will be reviewed with the principal investigator and signed prior to delivery hospitalization. Randomization will follow consent, and patients randomized to intervention will have teaching performed about how to use the device at the time of consent.

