## **6.0 Research Data Protection and Reporting**

### **6.1 Data Management and Confidentiality**

- A. Primary outcome measures of daily median pain scores will be compared using nonparametric statistical methods. Survey responses will also be compared using Chi-square for proportions, and non-parametric methods for ordinal data.
- B. Power analysis is not performed as this is a pilot study.
- C. No PHI will be recorded in any datasheet. Data sheets will be maintained in a password protected file on the password protected principle investigators' laptop.
- D. Because all data will be collected at the time of subject discharge, data should be complete and clean for each individual at the time of collection.

Version Number: 5

Protocol Number: Pro2018001008

PI Name: [name]

Protocol Title: TENS after Cesarean Delivery

13

RESERVED FOR IRB STAMP

DO NOT MODIFY THIS SPACE

IRB ID: Pro2018001008

Approval Date: 7/19/2022

Expiration Date: 7/18/2023

**E.** Data will be shared through University secure email among study investigators only. Source data will be destroyed following data analysis, anticipated to be 1 year after completion of study procedures.

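### No version of the primary pain analysis adjusts for pain before TENS starts; a defined pre-TENS score used as a covariate would usually sharpen the estimate, by an amount that depends on assumptions

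*SAP*

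**What the plan says.** The two documents describe the primary pain analysis in more than one way.

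- SAP, Primary Outcome: the arms are compared on "mean change in pain score as measured by Visual Analog Scale (VAS) over the course of the inpatient hospital stay". No starting or finishing time point for the change is given.
- Same SAP paragraph: "Fixed effects repeated measures analysis of variance was used to evaluate the differences in pain scores between groups". This sentence is about scores, not changes.
- SAP, Missing data: "Mixed-effects procedure was utilized to avoid loss of data from missing values at different time points". No covariates are named.
- Protocol 6.1, item A: "Primary outcome measures of daily median pain scores will be compared using nonparametric statistical methods".

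On timing, Protocol 1.3 says "Starting 8 hours after C-Section, the TENS unit will be turned on to a comfortable intensity as determined by the patient". Scores come from routine charting: "Our research team members will collect the following data points from the patient's inpatient medical record: pain scale scores". Allocation happens much earlier, at prenatal consent: "Randomization will follow consent, and patients randomized to intervention will have teaching performed about how to use the device at the time of consent". Protocol 1.5 plans 20 women, 10 per arm, with 5 per arm in each opioid-history group. No correlation, SD of change or power calculation is given.

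**The concern.** A change score needs a starting value, yet the plan neither defines one nor uses it as a covariate. Subtracting one noisy early score adds its error to every woman's outcome. Ignoring the early score discards information instead. Either way, a chance difference between the arms in early pain feeds into the estimated TENS effect.

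With 10 women per arm such differences are common, and the estimate with its interval is the main product of a pilot that Protocol 1.5 says will serve as the basis for larger trials. An estimate noisier than it need be would carry into that planning.

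**Working it through.** **Inputs.** From the documents: N = 20, 10 v 10 (Protocol 1.5); TENS start at hour 8 (Protocol 1.3). Assumed: correlation r between early and later scores of 0.3 to 0.7, equal SDs (set to 1), and one follow-up score, or six that are equally correlated with each other and with the early score. The plan has no figure of its own to reproduce.

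**Small-sample cost.** Estimating the covariate slope inflates variance by about 1 + 1/(N − 4): 1 + 1/16 = 1.0625 at N = 20, and 1 + 1/6 = 1.167 within a 10-woman stratum. Protocol 4.5 also gives 40 as the number to complete; the factor would then be 1 + 1/36 = 1.028.

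**One follow-up score.**
- Change score variance: 2(1 − r).
- Unadjusted later score variance: 1.
- Adjusted variance: (1 − r²) × 1.0625.
- Ratio to change: (1 + r)/2 × 1.0625.

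**Six scores.** The variance of their mean is v = (1 + 5r)/6, which is 0.417, 0.583 and 0.750 at r = 0.3, 0.5 and 0.7.
- Change: v + 1 − 2r = 0.817, 0.583, 0.350.
- Adjusted: (v − r²) × 1.0625 = 0.347, 0.354, 0.276.

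Variance of the adjusted estimate divided by that of the alternative, at N = 20:

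| r | v change, one score | v change, six | v unadjusted later, one score | v unadjusted later, six |
|---|---|---|---|---|
| 0.3 | 0.69 | 0.43 | 0.97 | 0.83 |
| 0.5 | 0.80 | 0.61 | 0.80 | 0.61 |
| 0.7 | 0.90 | 0.79 | 0.54 | 0.37 |

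At r = 0.2 with one score, the ratios are 0.64 against change and 0.96 × 1.0625 = 1.02 against unadjusted later scores, a slight loss. With one score, adjustment beats change while (1 + r) × 1.0625 < 2, that is r below 0.88.

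**Check by simulation** (6,000 replicates, against change, r = 0.3 / 0.5 / 0.7). At 10 v 10 variance fell by 31 / 19 / 8% with one score and 50 / 35 / 17% with the mean of three. At 5 v 5 with one score it fell by 25 / 15 / 1%.

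**Unequal SDs.** With one score, before the small-sample cost, the reduction against change is (s0 − r·s1)² / (s0² + s1² − 2r·s0·s1).
- Protocol 1.4, Table 1: pooled SDs are 0.292 on POD-0 and 0.231 on POD-1, giving 50 / 44 / 38%.
- The quartiles under Figure 1 in the same section imply SDs of 20/1.349 = 14.8 and 21.75/1.349 = 16.1 if normal, giving 30 / 19 / 9%.

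**Chance imbalance.** The probability of an early difference of at least 0.5 SD is 2(1 − Φ(0.5/√(2/n))): 26% at n = 10 per arm and 43% at n = 5. With one later score, a 0.5 SD imbalance moves the change estimate by (1 − r) × 0.5 and the unadjusted later estimate by r × 0.5. At r = 0.5 both are 0.25 SD.

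**Open allocation.** Suppose knowing the allocation shifts early scores in the TENS arm by d. As an estimate of the effect on later pain, the change score is off by the full d and the adjusted estimate by slope × d, which is less when the slope is below 1. Unadjusted later scores do not carry this term.

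**The case against.** Five points can be made against acting on this.

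1. *The comparator is unsettled.* A reader might infer that the plan is definitely an unadjusted change score. The documents do not settle that: the SAP model sentence concerns scores and Protocol 6.1 concerns daily medians. This stands, and the gain behaves differently by comparator: it shrinks with r against change and grows with r against unadjusted later scores. But no version contains a baseline term, so the omission is common to all of them.
2. *The early score may not exist.* It is tempting to say that every woman already has a pre-TENS score on file. Nothing schedules one; it is an inference from the hour-8 start and routine charting. This stands, and availability must be confirmed.
3. *The covariate is not pre-randomization.* Open allocation and device teaching come first, so early reports may reflect allocation. This stands as a limitation. It does not favour the change score, which is affected more when the slope is below 1.
4. *The sample is small.* Within a 10-woman stratum at r = 0.7 with one score, the ratio to change is 0.85 × 1.167 = 0.99, so the gain disappears. Pooling women with and without opioid replacement may also raise r, which shrinks the gain over change. This limits where the covariate should be used.
5. *This is a pilot with no power analysis, and the SAP is partly in the past tense.* Both are true. They lower the stakes and bear on how the adjusted analysis is labelled, but they do not make the unadjusted analysis better.

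**Conclusion.** The concern holds in a limited form. Neither document adjusts the primary pain comparison for pain before TENS. At N = 20, net of the lost degree of freedom and with equal SDs, adjustment lowers variance against a change score by about 31% falling to 10% (one score) or 57% falling to 21% (six scores) as r goes from 0.3 to 0.7. Against unadjusted post-TENS scores it lowers variance by about 3% rising to 46%, or 17% rising to 63%.

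These ranges rest on the assumed correlation, number of scores and SD ratio; none of the gains comes from the documents. A reader might go further and quote a single gain of several tens of per cent, obtained free. The documents do not support that: the gain can be near zero or slightly negative at the extremes of r, and the covariate inflates variance by about 6% overall and 17% within a stratum.

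**What to change.** In the SAP:

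- Reconcile the change, score and daily-median descriptions into one primary pain analysis.
- Define the pre-TENS score as the last charted score before hour 8, with the same window in both arms, and confirm that it is available for each woman.
- Model the scores after hour 8 in the repeated-measures or mixed model with that score as a covariate. Report the adjusted TENS minus usual-care difference with its 95% CI, and show change only descriptively.
- State how women with no early score are kept in the analysis.
- Use the covariate in the overall comparison rather than within the 10-woman strata.
- State that the score follows open randomization.
- If outcome data have already been analysed, label the adjusted analysis post hoc.

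The cost is SAP wording, a chart check for early scores, and one degree of freedom.

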#### 1.4 Preliminary Data

Preliminary data in 10 studies supports the use of high frequency TENS (>100 Hz) for pain relief post-Cesarean. Alves Lima et al (2014) compared the effectiveness of high frequency (100 Hz) and low frequency (4 Hz) TENS for pain relief post-Cesarean. High frequency TENS was more effective to reduce pain than low frequency TENS ( $p<0.05$ ). A review by Vance et al (2014) confirmed the superior effectiveness of high frequency TENS compared to low frequency TENS for acute post-surgical pain and for patients taking opioid medications. Since women after Cesarean Section in this study will have acute post-surgical pain and be prescribed opioid medications, high frequency TENS was selected for the study intervention.

Literature support exists for both continuous and 30-minute interval settings for the delivery of TENS after Cesarean Section for 24, 48 and 72 hours post-operatively. Six out of the 10 preliminary studies utilized continuous TENS rather than 30-minute intervals in order to increase the total dosage of electrical stimulation intervention delivered to patients after surgery over the inpatient hospital stay. While both continuous and interval settings of TENS have been shown to be therapeutically effective to reduce pain, differences in subjects' perception of comfort with TENS may exist between continuous and interval settings, with continuous being rated as more comfortable. This protocol has selected continuous TENS because: 1) continuous TENS has been shown to be as effective as 30-minute TENS intervals, and 2) continuous TENS may allow participants to receive a lower intensity electrical stimulation over a longer duration, thereby providing a comparable dosage of electrical stimulation over time when compared to a higher intensity over a shorter period of time (30-minutes). This distinction is important because women in this study will be experiencing acute post-surgical pain after Cesarean Section delivery. The research team has selected continuous TENS setting at a subject-selected intensity that is comfortable in order to afford participants the same therapeutic benefit as 30-minute interval TENS, which would be set at a higher sensory threshold intensity and which may not be as comfortable for participants in order to be therapeutically effective.

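### The SAP's primary pain outcome names no baseline, start or end, so read literally it mixes readings from before and during TENS over a period that differs by woman

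*SAP*

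**What the plan says.** The SAP (Primary Outcome) sets the primary comparison on "mean change in pain score as measured by Visual Analog Scale (VAS) over the course of the inpatient hospital stay". It names the model: "Fixed effects repeated measures analysis of variance was used to evaluate the differences in pain scores between groups". Its missing-data paragraph adds a mixed-effects procedure for values absent at some time points. It lists no time points, no baseline reading and no opening or closing hour.

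The protocol (1.3 Research Design and Methods) gives the intervention arm "usual care plus TENS therapy beginning 8 hours after C-section and continuing to discharge". The procedures in the same section repeat the 8-hour start and say that the unit "will remain on until the patient is discharged", apart from breaks. No hour or post-operative day is fixed for discharge.

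The protocol also has a different primary summary. Section 6.1 states: "Primary outcome measures of daily median pain scores will be compared using nonparametric statistical methods". It does not say which days count.

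**The concern.** A score taken before hour 8 cannot carry an effect of a device that has not been switched on. The SAP's wording takes in the whole stay and does not exclude those scores. It calls the outcome a change but gives no reference reading, so the early scores could be baseline, outcome or both. The period also closes at each woman's own discharge, so women with different stays contribute different stretches of recovery.

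With 20 women, the choice of baseline and window could alter the result, and the SAP leaves that choice to be made with data in hand. Protocol 1.5 says the pilot is to be the basis for larger trials, so an effect estimate that is attenuated or hard to interpret would carry into their planning.

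**Working it through.** Neither document gives a power, effect size or SD for this trial's pain outcome, so there is no planned figure to reproduce. The check asks how much the undefined window could matter.

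**Inputs from the documents**
- TENS start: hour 8 (protocol 1.3).
- Size: 10 TENS and 10 control, as 5 + 5 in each opioid-history group (protocol 1.5).
- Illustrative effect: protocol 1.4, Table 1, POD-1, 0.362 (SD 0.173, n = 26) against 0.532 (SD 0.280, n = 24).

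**Assumptions**
- Length of stay L is 48 to 96 h. The documents give none. Section 1.4 cites support for "delivery of TENS after Cesarean Section for 24, 48 and 72 hours post-operatively", but those are treatment durations, not stays.
- Readings are evenly spaced. The effect is zero before hour 8 and constant afterwards, and the SD is unchanged.
- Two-sided alpha is 0.05.

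**Step 1: illustrative effect.** Pooled SD = √[(25 × 0.173² + 23 × 0.280²)/48] = 0.231. Difference = 0.532 − 0.362 = 0.170. d = 0.170/0.231 = 0.74 (0.737 before rounding the SD). As an input check, the pooled t is −2.605 against −2.612 printed in Table 1, so the inputs are usable.

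**Step 2: early scores averaged in as outcome.** Pre-TENS share = 8/L. Diluted effect = d × (1 − 8/L). Power comes from the noncentral t with 18 degrees of freedom and noncentrality d × √(10/2).

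| Stay L | Pre-TENS share | Difference | d | Power |
|---|---|---|---|---|
| Outcome from hour 8 only | 0% | 0.170 | 0.74 | 0.345 |
| 48 h | 16.7% | 0.142 | 0.61 | 0.256 |
| 72 h | 11.1% | 0.151 | 0.66 | 0.284 |
| 96 h | 8.3% | 0.156 | 0.68 | 0.299 |

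**Step 3: early scores used only as baseline.** The pre-TENS share of the outcome is 0 and the effect stays at 0.170.

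**Step 4: sensitivity to charting.** If early charting is denser (assumed every 2 h to hour 8, then every 4 h), the pre-TENS share of readings is 4/(4 + 10) = 29% for 48 h and 4/(4 + 22) = 15% for 96 h. On the protocol's daily summary, if day 1 is the first 24 h after surgery, 8/24 = 33% of that day precedes TENS and later days are unaffected.

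**Step 5: unequal periods.** After hour 8, a 48 h stay leaves 40 h and a 96 h stay leaves 88 h, so the period averaged differs by 88/40 = 2.2-fold.

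**The case against.** The strongest reply is that a change score needs a baseline, and the natural one here is a score from before TENS. The early readings are then not outcome values and nothing is diluted. Even a change from the first post-operative score keeps the full effect at any on-TENS reading, because randomised arms have the same expected baseline. An early baseline adds variation, not bias. This stands, and it makes the dilution conditional. It does not remove the gap, because the SAP never says which reading is intended.

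Second, the formula in step 2 describes a plain average, whereas the SAP plans a repeated-measures model. In that model the loss depends on the time points and the contrast. This also stands, but the SAP names neither.

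Third, the mixed-effects sentence lets women with unequal numbers of readings contribute. That is partial cover. It sets no common period or contrast, and it does not mention discharge as a reason for absent readings. In Table 1 pain is almost flat from POD-1 to POD-2 (control 0.532 to 0.514, intervention 0.362 to 0.352). Late differences in discharge time may therefore shift the average little, although the fall from POD-0 to POD-1 is larger (0.668 to 0.532 and 0.612 to 0.362).

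Fourth, protocol 6.1 says that no power analysis is performed because this is a pilot, and the Table 1 trial combined interval TENS with physiotherapy. The power figures therefore show only the size of a possible loss and undermine no claim of the plan.

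**Conclusion.** The primary pain outcome lacks a baseline, a start and an end, and nothing elsewhere in the protocol or SAP supplies them. Taken at its word, it pools readings before and during TENS over a woman-specific period. Under the stated assumptions, the cost lies between no dilution (early readings as baseline only) and a loss of about 17% to 8% of the effect for stays of 48 to 96 h (early readings as outcome). Illustrative power in the second case is 26-30% instead of about 35%. Denser early charting would raise the loss.

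A reader might infer more than this:
- That the effect is diluted as a matter of fact. The SAP does not say that the early readings enter as outcome.
- That a third of the stay could precede TENS. This needs a 24 h stay, which fits poorly with the daily device checks and the post-operative day 1 dressing change in protocol 1.3.
- That TENS may change length of stay and so confound the outcome. Length of stay is neither a hypothesis nor an outcome in either document.

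**What to change.** In the SAP:

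1. Count only VAS readings from hour 8 after cesarean as outcome values.
2. In both arms, take the last charted score before hour 8 as baseline. Enter it as a covariate in the repeated-measures (mixed) model, in place of the undefined change score.
3. List the post-operative times that enter, and state the between-arm contrast at those common times, so that early discharge does not alter the period compared. Treat times after discharge as not observed.
4. Optionally add a fixed cut-off such as 48 h, best as a sensitivity analysis. As the primary window it would drop later readings, although the aim is TENS throughout the hospitalization. Still report readings to discharge.
5. Reconcile this outcome with the daily median pain score in protocol 6.1, naming one as primary.

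The cost is SAP wording. The scores come from charts the trial already reviews, and no treatment or visit changes. There are three small downsides. The baseline is recorded after allocation is known. Some women may lack a score just before hour 8, because neither document gives a charting schedule, so a rule for that case is needed. The SAP, dated 7/11/2024, is partly in the past tense, so the change should carry its own date and say whether data had been reviewed by then.
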